8.3.13.5 Device Deficiencies

A device deficiency form will be completed and sent to the sponsor for all observed device malfunctions or deficiencies, including defects in devices that have not been implanted in a subject or used otherwise. Starting with the implantation of the ARGOS-SC implant, all relevant malfunctions will also be recorded in the subject's chart and CRF.

8.3.13.6 Acceptance Questionnaires ARGOS-SC

In the study, three types of questionnaires will be used to assess potential strengths and weaknesses of the ARGOS-SC system. Surgeons are asked to complete an implantation procedure questionnaire after each implantation at V01 (D0). At V09 (D360), the investigator responsible for IOP measurement

as well as the patients will be asked to complete a user acceptance questionnaires for the MESOGRAPH reading device and the general measurement procedure.

The aim of these questionnaires is to gain more information about the level of user-acceptance of the ARGOS-SC system during implantation and during IOP measurement. The data collected with these questionnaires is only of exploratory nature and will not be included in the analysis. Results will provide the sponsor with data that could influence future device system improvements.

8.3.13.7 National Eye Institute – Vision related Quality of Life Questionnaire-25 (VFQ-25)

The VFQ-25 is a standardized questionnaire about quality of life relating to the patient's vision. It should be completed by the patient at V06, V07 and V09.

8.3.13.8 Visual Acuity (VA)

The best corrected visual acuity will be determined after objective and subjective determination of refraction with the ETDRS chart in accordance with the ETDRS protocol. The number of character read and the reading distance will be recorded. The standard testing distance is 4 meters.

8.3.13.9 Visual Field (Perimetry)

The purpose of visual field testing is to determine both the outer limits of visual perception by the peripheral retina and the varying qualities of vision within that area. Perimetry is performed to obtain an accurate examination of the peripheral extent of the visual field. Automated perimeters will be used either with standard glaucoma field, field 30-2 or equivalent. This should always be done on **both eyes** in order to compare study and fellow eye.

A change of the perimeter during the study should be avoided.

8.3.13.10 External Eye Photography

External eye photography will be performed through a slit lamp camera or equivalent in order to document potential changes to the outer eye at Screening and V04 through V09.

8.3.13.11 Heidelberg Engineering ANTERION® (if available)

The ANTERION[®] from Heidelberg Engineering will be used for determination of the ARGOS-SC location at V04 through V09 (only at sites where it is available).

Page 63 of 97

8.3.13.12 Anterior eye segment measurement

Slit-lamp biomicroscopy (undilated, anterior segment)

At every visit, the external ocular structures and the front of the eye will be assessed using the slit-lamp biomicroscopy according to standard site procedures. Particular attention will be paid to the ocular surface and possible effects of the ARGOS-SC. The following structures will be assessed:

- a) Lids
- b) Conjunctiva (irritation)
- c) Cornea
- d) Anterior chamber (cells/flares (SUN-Classification), fibrin, flattening)
- e) Iris
- f) Pupil
- g) Lens
- h) Anterior vitreous body (cells/haze (NIH-Grading))

Optical Coherence Tomography (OCT)

Anterior Segment OCT will be used to evaluate effects on change in chamber angle and after nonpenetrating glaucoma surgery and to assess the central corneal thickness (Screening, V04 through V09).

Gonioscopy

Standard gonioscopy will be used to confirm glaucoma classification and to assess other problems within the anterior chamber, such as the presence of foreign bodies hidden in the recess of the angle. The gonioscopic grading system according to Shaffer is used in this study (Screening, V06, V07, V09).

8.3.13.13 Posterior eye segment measurement

Biomicroscopy (dilated, fundus)

The posterior eye segment will be examined using a slit lamp in combination with a 90D or "Superfield" or comparable lenses. The following parameters will be assessed:

- a) Optic nerve lesions
- b) Other posterior pole lesions
- c) Vitreous opacities
- d) Optic nerve head

- e) Fundus lesions
- f) Retinal arteries and veins (AV)
- g) Macular area
- h) Fundus periphery
- i) Normal and abnormal variations of the fundus.

Optical coherence tomography (OCT)

Posterior segment OCT will be used to assess both macular structures and the peripapillary nerve fiber layer (RNFL) at Screening, V06, V07 and V09.

If available, the Heidelberg Engineering Spectralis Glaucoma-Module Premuim Edition (Minimum rim width at Bruch membrane opening ((BMO-MRW), RNFLT and macula) should be used. This should always be done on **both eyes** in order to compare study and fellow eye.

Fundus photography

Standard fundus photography will be performed at Screening and V06, V07, 08 and V09 to document potential changes to the interior surface of the eye, including the retina. Additionally, a photo of the optic nerve and nerve fiber layer will be performed in red-free illumination.

8.3.13.14 Intraocular pressure (IOP) measurement

Intraocular pressure will be measured using three techniques. Goldmann Applanation Tonometry (GAT) will be performed in the clinic at every visit and if available, Pascal Dynamic Contour Tonometry (DCT) at V05 through V09. ARGOS-SC measurements will be performed in the clinic at every visit and by the patient at home between the visits. Only GAT will be used to guide any treatment decisions. The GAT and DCT must be performed by as few dedicated investigators as possible at each site to reduce potential bias.

IOP measurement in the clinic

IOP measurement will be conducted at V02 through V09 as a series of 2x GAT (in case of a difference of more than 2mmHg, a third GAT-measurement is required) followed by 3x ARGOS-SC system. When series of measurements are made, GAT must always be used first to avoid potential operator bias. For the ARGOS-SC measurements the patient has to stay in the same position as for the GAT-measurements (chin on chin rest, forehead installed). From V05 through V09 additionally (if available), a series of 2x DCT (in case of a difference of more than 2mmHg, a third DCT-measurement is required)

followed by 3x ARGOS-SC will be performed after the series of GAT and ARGOS-SC measurements. For the ARGOS-SC measurements, the patient has to stay in the same position as for the DCT-measurements (chin on chin rest, forehead installed).

Optional: At V06, V07 and V09, the patient will be hospitalized for 24-hours measurements with GAT and ARGOS-SC. IOP measurements with ARGOS-SC will be done automatically via an external antenna. IOP measurements with GAT will be done every three hours, if it is possible even at night. If night measurements are not possible every three hours at night, the last measurement should take place between 22 and 24 o'clock and the three-hours rhythm should be resumed between 5 and 7 o'clock on the next morning.

ARGOS-SC system measurement by the subject at home

Subjects will receive detailed instruction in the use of the MESOGRAPH reading device. At V02, they will receive an individual MESOGRAPH reading device, a copy of the instructions for use and the Multiline Connector to perform self-tonometry at home. Subjects will be requested to perform at least 4 IOP measurements daily with the MESOGRAPH, one each in the morning after getting up, at noon, in the afternoon and in the evening before going to bed.

No data will be recorded manually by the subject. The MESOGRAPH reading device, which is capable of storing up to 3,000 measurements, will be connected to an external GSM module, which will transfer the measured value directly to a secure database. Investigators can log into the database in order to track the pressure levels of their patients as required.

The MESOGRAPH will also be brought to every visit, at which time site staff will assess its functionality and delete recorded IOP data from its memory.

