8.1.2 Description of the measures to be taken to minimize or avoid bias

No randomization or blinding/masking procedures will be used in this study. To avoid bias resulting from patient selection, all consecutive patients who potentially meet the eligibility requirements will be informed of the study and asked to participate. Those agreeing will undergo the informed consent procedure and if they consent, will be screened. All eligible patients will be enrolled.

There will be no control group for safety events. Incidence, nature and severity will be compared to literature of standalone NPGS. To allow assessment of performance, measurements of IOP with the ARGOS-SC sensor will be compared to those obtained with the standard GAT method and Pascal DCT at the same time point. To prevent possible influence of prior knowledge of the IOP value obtained with the ARGOS-SC, which is objectively displayed, measurements will always be made first with GAT/DCT. Data on all device deficiencies will be recorded.

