8.3.12 Performance

IOP level will be assessed at every follow-up visit in a series of 2 GAT standard measurements followed by 3 consecutive measurements with the ARGOS-SC system. From V05 (day 30) on, if available, additional 2 DCT measurements followed by 3 consecutive measurements with the ARGOS-SC system. **Optional:** At visits V06, V07 and V09, 24-hours measurements with GAT and ARGOS-SC will be done inpatient.

Patients will be given a MESOGRAPH reading device at Visit 01 in order to measure the IOP daily at home. Measurements shall be taken at least 4 times per day (morning, noon, afternoon, evening). The MESOGRAPH reading device will be connected to an external GSM module, which will transfer the measured value directly to a secure database. Investigators can log into the database in order to track the pressure levels of their patients as required. At every follow-up visit, site staff will examine the subject's hand-held reader device and download all readings recorded since the last visit. In addition, they will ask subjects non-leading questions to determine if any device deficiencies occurred since the last visit. All device deficiencies will be recorded on the device deficiency page of the CRF.

To ensure accuracy and comparability of the recorded parameters, all responsible site personnel will be thoroughly instructed on the agreed measurement methods.

To access the user acceptance of the implantation procedure and the general usability of the ARGOS-SC system, surgeons and personnel performing the ARGOS-SC system measurements will be asked to complete user acceptance questionnaires. The aim of these questionnaires is to gain more information about the level of user-acceptance of the ARGOS-SC system during implantation and during IOP measurement. The data collected with these questionnaires is only of exploratory nature and will not be included in the analysis. Results will provide the sponsor with data that could influence future device system improvements.

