- ¹² V02 to V09 IOP measurements will be made in series of 2 GAT measurements (in case of a difference of more than 2 mmHg, a third GAT measurement is required) followed by 3 directly consecutive ARGOS-SC system measurements; *if DCT is available:* V05 to V09 additionally followed by 2 Pascal DCT measurements (in case of a difference difference of more than 2 mmHg, a third Pascal DCT measurement is required) and 3 directly consecutive ARGOS-SC system measurements.
- ¹³ Optional: Patient's admission at the site for a 24h series of measurements with GAT and ARGOS-SC sensor. Measurements with EYEMATE-SC sensor will be done automatically via an externa antenna. GAT will be done every three hours, if it is possible even at night. If night measurements are not possible every three hours at night, the last measurement should take place between 22 and 24 o'clock and the three-hours rhythm should be resumed between 5 and 7 o'clock on the next morning.
- ¹⁴ All patients will receive a MESOGRAPH reading device after implantation in order to measure the IOP daily at home. Measurements will be taken at least 4 times per day (morning, noon, afternoon, evening). The MESOGRAPH reading device will be connected to an external GSM module, which will transfer the measured value directly to a secure database. Investigators can log into the database in order to track the pressure levels of their patients as required.

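### At V05–V09 the DCT readings follow a displayed ARGOS-SC series on the same eye, so the protocol's tonometer-first safeguard is not carried through for DCT

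*Protocol*

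**What the plan says.** **The safeguard.** Protocol 8.1.2 gives its reason, "To prevent possible influence of prior knowledge of the IOP value obtained with the ARGOS-SC", and then the rule: "which is objectively displayed, measurements will always be made first with GAT/DCT". The rule names DCT as well as GAT. The same section excludes other protection: "No randomization or blinding/masking procedures will be used in this study".

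**The sequence.** Protocol 8.3.13.14 has GAT followed by three ARGOS-SC readings at every follow-up visit. From V05 to V09, where DCT is available, a DCT series "followed by 3x ARGOS-SC will be performed after the series of GAT and ARGOS-SC measurements". The order rule in that section mentions GAT alone: "When series of measurements are made, GAT must always be used first to avoid potential operator bias". Table 1 note 12 (section 8.3.15) has the same order, "V05 to V09 additionally followed by 2 Pascal DCT measurements", and 8.3.12 adds to the GAT and ARGOS-SC series an "additional 2 DCT measurements followed by 3 consecutive measurements with the ARGOS-SC system". The corresponding footnote to the SAP flow chart (2.10) repeats it.

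**The role of DCT.** Agreement with DCT is in the primary objective (protocol 7.1.1, SAP 2.7.1) and, from V05 on, in the primary endpoint (protocol 8.1.3.1). SAP 2.9.1 evaluates it in the same way as GAT. The pass/fail rule in protocol 9.5 refers to GAT and ARGOS-SC only.

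**The concern.** The purpose of 8.1.2 is that nobody takes a tonometer reading while knowing what the sensor shows for that eye. The V05–V09 sequence achieves this for GAT. For DCT it does not: three sensor readings have just been taken and displayed for the same eye in the same session.

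If the DCT operator knows those values, the DCT readings may be drawn towards them, and the DCT comparison would then look better than it should. This matters because protocol 8.2.2 presents DCT as free of some of GAT's corneal error and as believed to be closer to true IOP. It is the comparison least open to the argument that disagreement is the reference method's fault. Every scheduled DCT pair has the same exposure, so the planned visits contain no unexposed DCT pairs for a sensitivity analysis.

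**Working it through.** The plan states no figure on this point. The main check sets the sections side by side.

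**1. Order at V05–V09 (protocol 8.3.12, 8.3.13.14, Table 1 note 12; SAP 2.10)**

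| Step | Measurement | Sensor value already displayed this session? |
|---|---|---|
| 1 | GAT ×2 (third if the two differ by more than 2 mmHg) | No |
| 2 | ARGOS-SC ×3 | – |
| 3 | DCT ×2 (third if the two differ by more than 2 mmHg) | Yes, up to three values |
| 4 | ARGOS-SC ×3 | – |

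The rule in 8.1.2 is met at step 1. At step 3 it is met only if it is read as tonometer before sensor within each analysed pair. Its stated purpose is not met.

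**2. Other protection.** There is none in the text. Masking is excluded in 8.1.2. Section 8.3.13.14 asks for as few GAT and DCT examiners as possible, but does not require a separate DCT examiner or a hidden display.

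**3. Number of pairs exposed.** The inputs are 24 patients (protocol 8.3.7) and five DCT visits, V05 to V09 (Table 1). 24 × 5 = 120 pairs at most, all of which follow an ARGOS-SC series. The match with the minimum of about 120 measurements in protocol 9.2 is a coincidence.

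**4. Illustration of the mechanism, not an estimate.** Suppose the DCT reading moves a fraction *w* of the way to the sensor value, and ignore drift between the two sensor series:

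DCT′ = (1 − *w*)·DCT + *w*·ARGOS, so ARGOS − DCT′ = (1 − *w*)(ARGOS − DCT).

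The mean *m* and SD *s* of the differences both shrink by (1 − *w*). With normal differences,

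share within ±5 mmHg = Φ[(5 − (1 − *w*)*m*) / ((1 − *w*)*s*)] − Φ[(−5 − (1 − *w*)*m*) / ((1 − *w*)*s*)].

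The documents give neither *w* nor a DCT difference SD. Rows one and two borrow the GAT differences at V05 and V06 in the SAP's mock-up Table 2. Row three is assumed.

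| Mean, SD (mmHg) | *w* = 0 | 0.10 | 0.25 | 0.50 |
|---|---|---|---|---|
| 1.91, 3.38 | 79.9% | 84.6% | 91.5% | 99.1% |
| 0.41, 4.39 | 74.3% | 79.2% | 86.9% | 97.7% |
| 0, 5.0 | 68.3% | 73.3% | 81.8% | 95.4% |

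For example, in row three with *w* = 0.10 the SD becomes 0.90 × 5.0 = 4.5, and 5/4.5 = 1.11 gives 73.3%. The direction is built into the assumption. The table shows only that a modest pull, if there is one, would move the share within 5 mmHg that SAP 4.6.1 reports for DCT.

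**The case against.** **The pairing.** The SAP compares DCT with the second ARGOS-SC series (4.6.1), and DCT does precede that series. The order also keeps each tonometer next to its own sensor series with the patient in the same position, which is a sound reason for it. This stands as a defence of the order. It does not meet the purpose stated in 8.1.2, because the earlier series has already shown the sensor's reading of that eye.

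**Whether the operator sees the values.** A reader might infer that the DCT operator has necessarily seen them. The documents do not say so. Protocol 4.6 lets any trained person, including the patient, take ARGOS-SC readings, and no section says who watches the display. The text supports only that the operator may have seen them.

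**The third DCT reading.** A reader might infer that a biased operator decides whether to take it. In fact a fixed difference of more than 2 mmHg triggers it. Any influence would have to act through the readings themselves.

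**Direction and size.** It is tempting to say that knowledge of the sensor value can only improve agreement. That is unsupported: the operator also knows the GAT values, and protocol 8.2.2 describes DCT as less prone to user error, though not immune. A pull towards the sensor value is the expected direction, but it is not demonstrated.

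**Reach.** It would be wrong to infer that the trial's success decision is compromised. Protocol 9.5 uses GAT, and GAT precedes any sensor reading in each scheduled clinic series.

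**Conclusion.** The point holds as an internal inconsistency with a plausible route to bias. Protocol 8.1.2 promises for DCT a protection that 8.3.12, 8.3.13.14, Table 1 note 12 and the SAP footnote do not deliver.

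The consequence is confined to the DCT part of the primary objective and endpoint. The exposure ceiling is 120 pairs; the actual number is unknown, because DCT is done only where available and patients who drop out after implantation are not replaced. Exposed does not mean biased, and a reader should not take 120 as a count of distorted pairs.

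The expected direction, towards better apparent agreement, rests on two assumptions: that the DCT operator sees the first sensor series, and that knowing it pulls the DCT reading towards it. It is worth correcting because the comparison is a stated primary one and the remedy is cheap.

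**What to change.** Keep the order, so that GAT stays next to its sensor series, and add one requirement: the DCT operator does not see the first ARGOS-SC values until the DCT readings are recorded. State it consistently in protocol 8.1.2, 8.3.12, 8.3.13.14 and Table 1 note 12, and in the matching SAP 2.10 footnote.

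The documents do not say that the display can be switched off, so the instruction should not depend on that. The patient, or another trained person already present, can hold the reader with the display covered or turned away. The reader stores its measurements (8.3.13.14) and staff download them at each visit (8.3.12), so the first series can be recovered afterwards. Because 8.3.13.14 also has staff delete the stored data at visits, the instruction must require readout before deletion.

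The cost is a handling instruction, a sentence in each section and slightly later transcription of the first sensor series. One limit remains: investigators can view home readings in the database, and this change does not remove that prior knowledge.

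Moving both tonometers ahead of all sensor readings would also satisfy 8.1.2, but it would separate GAT from its paired sensor series, which is the comparison that decides success.

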8.3.14 Surgery

During the first implantations and if desired, a member of Implandata staff will be present at the surgery.

8.3.14.1 Non-penetrating glaucoma surgery and preparation for implantation

At the start of the procedure, the conjunctiva is excised over 2 clock hours around the limbus next to the proposed operation side after which the non-penetrating glaucoma surgery is performed using the surgeon's normal preferred procedure. Because the ARGOS-SC sensor will be placed in the suprachoroidal space following completion of the IOP lowering portion of the non-penetrating glaucoma surgery, hyaluronic acid-based viscoelastics such as Healon OVD (Abbott Medical Optics Inc.) should be used to separate the sclera from the choroid. This additionally serves as a safeguard against injuries of the surrounding tissue. Viscoelastics based on hydroxpropyl methylcellulose (HMPC) or other synthetic or semi-synthetic alternatives to hyaluronic acids are to be avoided.

8.3.14.2 ARGOS-SC pressure sensor implantation

To ensure proper function of the sensor when implanted, it is critical to confirm before implantation that the ASIC is in the proper orientation. Care must be taken throughout the process to avoid damaging the ASIC. The sensor may only be handled using the specially designed implantation forceps (Implandata Ophthalmic Products GmbH, Germany), the tips of which are padded with silicone to protect the microsensor from damage and facilitate its implantation.

A scleral window of at least 3.2 to 3.5 mm (maximum 4x4 mm) is necessary for the implantation of the sensor. If a narrower scleral flap was used for the IOP lowering surgery, the width of the flap will be enlarged or an additional small incision made next to it to ensure a final width of at least 3.2 mm.

Using the specially designed implantation forceps, the implant is pushed gently through the scleral opening into the suprachoroidal space with the "pressure sensing side" of the ASIC facing the eye. The sensor must not be forcibly inserted.

For the detailed ARGOS-SC implantation process, please see "IFU ARGOS-SC Implant".

8.3.14.3 ARGOS-SC pressure sensor explantation, if medically necessitated

In the event that the sensor must be explanted, a scleral incision of 4.5 to 5 mm is made above the pars plana at the short side of the sensor, preferably above it. The incision must be fully opened to

Page 67 of 97

ensure a safe explantation procedure. A hyaluronic acid-based viscoelastic (see implantation) is then inserted in the suprachoroidal space to ensure complete separation of the sclera and the choroid. Following explantation, the scleral incision should be sealed using at least one suture. The explanted device is to be returned to Implandata Ophthalmic Products GmbH for analysis. For the detailed ARGOS-SC explantation, please see *"IFU ARGOS-SC Implant*).

8.3.15 Study Visits

Assessments and procedures to be performed at each visit are indicated with an X in the assessment schedule in Table 1 (see also Section 8.3.13 Assessments). The visits should be arranged as closely as possible to the specified visit day, accepted tolerances are set up for every visit (see Table 1).

Clinical Investigation Plan ARGOS-SC01

Page 68 of 97

Table 1: Assessment Schedule ARGOS-SC01

Visit	SC	V01	V02	V03	V04	V05	V06	V07	V08	V09
Indicative Days (D) Visit window	Up to 28 days before surgery	D0	D1	D3 - 1/+ 2 Days	D10 +/- 1 Day	D30 +/- 5 Days	D90 +/- 10 Days	D180 +/- 15 Days	D270 +/- 15 Days	D360 +/- 15 Days
GENERAL										
Informed consent signed	х									
Allocation of subject number	х									
Inclusion & exclusion criteria	х	X^1								
Demography	х									
Past and current significant medical history	х									
Pregnancy test (urine beta- hCG)	х	X ²								
Non-penetrating glaucoma surgery and ARGOS-SC pressure sensor implantation		х								
Vision related Quality of Life (VQoL) questionnaire	х						х	х		х
Visual acuity (ETDRS) ³	х		х	Х	Х	х	х	х	Х	Х
Perimetry ⁴ (OU)	х						х	Х		Х
Heidelberg Engineering ANTERION®					Х	х	х	х	х	х
External eye photography⁵	Х				Х	Х	Х	Х	Х	Х
Implantation procedure questionnaire (surgeon)		х								
User acceptance questionnaire (patient)										х
User acceptance questionnaire (investigator)										х
Concomitant medication	х	х	х	х	Х	х	х	х	Х	х
AE/ADE/SAE/SADE		х	х	х	х	х	х	х	х	х
Device malfunction		х	х	х	Х	х	х	х	х	х
ANTERIOR SEGMENT										
Optical Coherence Tomography ⁶	х				Х	х	х	х	х	х
Slit-lamp biomicroscopy ⁷	х		х	Х	Х	х	х	Х	х	Х
Gonioscopy ⁸	х						х	Х		х
POSTERIOR SEGMENT										
Slit-lamp biomicroscopy ⁹	х		Х	Х	Х	Х	Х	Х	Х	Х
Optical coherence tomography (OCT) ¹⁰ (OU)	х						х	х		х
Fundus photography ¹¹	х						х	х		х

Clinical Investigation Plan ARGOS-SC01

Page 69 of 97

Visit	SC	V01	V02	V03	V04	V05	V06	V07	V08	V09
Indicative Days (D)	Up to 28 days before surgery	DO	D1	D3 - 1/+ 2 Days	D10 +/- 1 Day	D30 +/- 5 Days	D90 +/- 10 Days	D180 +/- 15 Days	D270 +/- 15 Days	D360 +/- 15 Days
IOP Measurement										
Goldmann Applanation Tonometry ¹²	х		х	х	х	х	х	х	х	х
Pascal Dynamic Contour Tonometry ¹²	х					х	х	х	х	х
ARGOS-SC pressure sensor measurement ¹²			х	х	х	х	х	х	х	х
Optional:										
24-hours measurements							х	х		х
inpatient with GAT and ARGOS-SC over 24h ¹³										
ARGOS-SC pressure sensor self-measurement ¹⁴		Х	х	х	х	х	х	х	х	х

¹ Eligibility must be reassessed at V01 prior to surgery.

² For females of childbearing potential, a pregnancy test performed within 24 hours preceding surgery must be negative to confirm eligibility.

³ The best corrected visual acuity will be determined after objective and subjective determination of refraction with the ETDRS chart in accordance with the ETDRS protocol.

⁴ Perimetry is performed to obtain an accurate examination of the peripheral extent of the visual field. Automated perimeters will be used either with standard glaucoma field, field 30-2 or equivalent.

- ⁵ External eye photography is performed through a slit lamp camera or equivalent. The outer eye shall be photographed in order to document potential changes to the iris or pupil structure.
- ⁶ Anterior segment OCT is performed to evaluate effects on change in chamber angle after non-penetrating glaucoma surgery and to assess corneal thickness.

⁷ Slit-lamp biomicroscopy is performed through an undilated pupil to assess the following anatomic parameters of the anterior segment: lids, conjunctiva, cornea, anterior chamber, iris, pupil, lens and anterior vitreous body.

- ⁸ Standard gonioscopy is used to confirm glaucoma classification and to evaluate the presence of iris tumors, foreign bodies, anterior synechiae and to predict the anterior chamber angle. The gonioscopic grading system according to Shaffer is used in this clinical investigation.
- ⁹ Posterior segment biomicroscopy is performed by means of indirect ophthalmoscopy on a slit lamp with the aid of a 90D or "Superfield" or comparable lenses. For this examination the pupil needs to be dilated by the use of mydriatic agents. This method is used to evaluate the following parameters: optic nerve lesions, other posterior pole lesions, vitreous opacities, optic nerve head, fundus lesions, retinal arteries and veins (AV), macular area, fundus periphery, normal and abnormal variations of the fundus.
- ¹⁰ Posterior segment OCT is used to assess macular structures and the peripapillary nerve fiber layer thickness (RNFLT) and if possible Minimum rim width at Bruch membrane opening (BMO-MRW).
- ¹¹The fundus should be photographed in order to document potential changes to the optic nerve (cup/disc ratio) and nerve fiber layer (red-free illumination).
- ¹² V02 to V09 IOP measurements will be made in series of 2 GAT measurements (in case of a difference of more than 2 mmHg, a third GAT measurement is required) followed by 3 directly consecutive ARGOS-SC system measurements; *if DCT is available:* V05 to V09 additionally followed by 2 Pascal DCT measurements (in case of a difference difference of more than 2 mmHg, a third Pascal DCT measurement is required) and 3 directly consecutive ARGOS-SC system measurements.
- ¹³ Optional: Patient's admission at the site for a 24h series of measurements with GAT and ARGOS-SC sensor. Measurements with EYEMATE-SC sensor will be done automatically via an externa antenna. GAT will be done every three hours, if it is possible even at night. If night measurements are not possible every three hours at night, the last measurement should take place between 22 and 24 o'clock and the three-hours rhythm should be resumed between 5 and 7 o'clock on the next morning.
- ¹⁴ All patients will receive a MESOGRAPH reading device after implantation in order to measure the IOP daily at home. Measurements will be taken at least 4 times per day (morning, noon, afternoon, evening). The MESOGRAPH reading device will be connected to an external GSM module, which will transfer the measured value directly to a secure database. Investigators can log into the database in order to track the pressure levels of their patients as required.

